Attachment 9: Eastern Cooperative Oncology Group (ECOG) Performance Status

ECOG Grade Scale (with Karnofsky conversion)

- Fully active, able to carry on all predisease performance without restriction. (Karnofsky 90-100)
- 1 Restricted in physically strenuous activity but ambulatory and able to carry out work on a light or sedentary nature, eg, light housework, office work. (Karnofsky 70-80)
- Ambulatory and capable of all self-care but unable to carry out any work activities. Up and about more than 50% of waking hours. (Karnofsky 50-60)
- Capable of only limited self-care; confined to bed or chair more than 50% of waking hours. (Karnofsky 30-40)
- 4 Completely disabled. Cannot carry on any self-care. Totally confined to bed or chair. (Karnofsky 10-20)
- 5 Dead. (Karnofsky 0)

Attachment 10: Screening Myelofibrosis (MF) Symptom Form

Instructions to Subjects: Please answer all questions to the best of your ability, based on your memory over the past 7 days (1 week). There is no right or wrong answer.

1. During the past 7 days, how severe were your worst night sweats (or feeling hot or flushed) due to MF?

0 (Absent) 1 2 3 4 5 6 7 8 9 10 (Worst Imaginable)

2. During the past 7 days, how severe was your worst itchiness due to MF?

0 (Absent) 1 2 3 4 5 6 7 8 9 10 (Worst Imaginable)

3. During the past 7 days, how severe was your worst abdominal discomfort (feel uncomfortable, pressure or bloating) due to MF?

0 (Absent) 1 2 3 4 5 6 7 8 9 10 (Worst Imaginable)

4. During the past 7 days, how severe was your worst pain under the ribs on the left side due to MF?

0 (Absent) 1 2 3 4 5 6 7 8 9 10 (Worst Imaginable)

5. During the past 7 days, at its worst, to what degree did you feel full quickly (early satiety) after beginning to eat due to MF?

0 (Not at all) 1 2 3 4 5 6 7 8 9 10 (Worst Imaginable)

6. During the past 7 days, how severe was your worst bone or muscle pain due to MF (diffuse, not joint or arthritis pain)?

0 (Absent) 1 2 3 4 5 6 7 8 9 10 (Worst Imaginable)

7. During the past 7 days, how severe was your worst inactivity (including work and social activities) due to MF?

0 (Absent) 1 2 3 4 5 6 7 8 9 10 (Worst Imaginable)

ALP	alkaline phosphatase
ALT	alanine aminotransferase
AST	aspartate aminotransferase
BM	bone marrow
CI	clinical improvement
CR	complete remission
DMC	Data Monitoring Committee
DNA	deoxyribonucleic acid
ECG	electrocardiogram
ECOG	Eastern Cooperative Oncology Group
eCRF	electronic case report form
EQ-5D-5L	EuroQol-EQ-5D-5L
FDA	Food and Drug Administration
GCP	Good Clinical Practice
GGT	gamma-glutamyl transpeptidase
Hb	hemoglobin
HI-E	hematologic improvement-erythroid
HIV	human immunodeficiency virus
HR	heart rate
hTERT	human telomerase reverse transcriptase
IB	Investigator's Brochure
ICF	informed consent form
ICH	International Conference on Harmonisation
IEC	Independent Ethics Committee
INR	international normalized ratio
IPSS	International Prognostic Scoring System
IRB	Institutional Review Board
IRR	infusion related reaction
ITT	intent to treat
IV	intravenous
IWG	International Working Group
IWG 2006	International Working Group Response Criteria [in Myelodysplasia] 2006
IWG-MRT	International Working Group – Myeloproliferative Neoplasms Research and Treatment
IWRS	interactive web response system
LFT	liver function tests
MDS	myelodysplastic syndrome(s)
MedDRA	Medical Dictionary for Regulatory Activities
MF	Myelofibrosis
NCI-CTCAE	National Cancer Institute Common Terminology Criteria for Adverse Events
OS	overall survival
PD	progressive disease / disease progression
PE	physical exam
PK	pharmacokinetic(s)
PR	partial remission
pRBC	packed red blood cell
PRO	patient-reported outcome(s)
PT	prothrombin time
qRT-PCR	quantitative real-time polymerase chain reaction
RBC	red blood cell
RNA	ribonucleic acid
SIPPM	Site Investigational Product Procedures Manual
SVR	spleen volume reduction
TA	telomerase activity

TI	transfusion independence
TL	telomere length
ULN	upper limit of normal
WHO	World Health Organization

1. INTRODUCTION

This statistical analysis plan contains definitions of analysis populations, derived variables and statistical methods for analysis of efficacy and safety.

1.1. Trial Objectives

The primary objective of this study was to evaluate spleen response rate and symptom response rate of 2 dose regimens of imetelstat (9.4 mg/kg and 4.7 mg/kg imetelstat given intravenously [IV] every 3 weeks) in subjects with intermediate-2 or high-risk myelofibrosis (MF) who are relapsed after or refractory to JAK inhibitor treatment.

Secondary objectives were to assess the safety of imetelstat; to assess complete remission (CR) or partial remission (PR), clinical improvement (CI), spleen response, symptoms response and anemia response per modified 2013 International Working Group – Myeloproliferative Neoplasms Research and Treatment (IWG-MRT) criteria, duration of responses, and overall survival (OS); to evaluate the pharmacokinetics (PK) of imetelstat; to evaluate the PK/response and pharmacodynamic (PD) relationships with factors that include hemoglobin concentration, spleen size, and platelet count; to evaluate the immunogenicity of imetelstat; and to assess the effect of treatment on patient-reported outcomes (PROs).

The exploratory objectives were to assess the PK relationship with telomerase activity (TA), telomere length (TL) or human telomerase reverse transcriptase (hTERT), to characterize the baseline cytogenetic and mutational status for their association with clinical response, and to evaluate the change of cytogenetic abnormalities or mutant allele burden for assessing cytogenetic and molecular responses.

1.2. Trial Design

This was a randomized, single-blind, multicenter, Phase 2 study of 2 dosing regimens of single-agent imetelstat in subjects with intermediate-2 or high-risk MF (primary MF [PMF], post-ET--MF [PET-MF], or post-PV-MF [PPV-MF]) who were relapsed after or refractory to JAK inhibitor treatment. Eligible subjects were stratified based on a) spleen size ≥ 15 cm below the left costal margin (yes vs. no) and b) platelet count at study entry (platelets $\geq 75 \times 10^9/L$ and $< 150 \times 10^9/L$ vs. $\geq 150 \times 10^9/L$). Study treatment was administered on a 21-day cycle. The main study had phases: a screening phase of up to 21 days before randomization; a treatment phase extended from randomization until

study drug discontinuation; and a posttreatment follow-up phase that began when the subject discontinued imetelstat. The posttreatment follow-up phase would continue until death, lost to follow-up, withdrawal of consent or study end, whichever occurred first. The end of study was defined as 18 months after the last subject was enrolled or when the sponsor terminated the study, whichever occurred first.

With Protocol Amendment 3, the study has been closed to further subject enrollment. Subjects in the Treatment Phase who benefited from study treatment may enter an Extension Phase and continue to receive imetelstat until there was loss of benefit or unacceptable toxicity, as determined by the investigator according to local standard of care. Subjects in the Posttreatment Follow-up Phase will enter the Extension Phase to continue follow-up for survival status. The Extension Phase will end approximately 1 year after the clinical cutoff for the final analysis of the main study.

The first interim review planned in this study occurred after the first 40 evaluable subjects (defined as the subjects who have both baseline and post baseline spleen measurement per investigator MRI, 20 per treatment arm) were followed for at least 12 weeks. Both arms would continue with enrollment until approximately 100 subjects per arm were enrolled if both of them were efficacious and had an acceptable safety profile. If only one arm was efficacious and had an acceptable safety profile, then that arm would continue enrollment and enrollment would be stopped in the other arm. In the case that both arms were not efficacious and safe, an alternative dose may be selected based on the PK/PD exposure-response, efficacy, and safety analysis and a protocol amendment would be implemented to reflect this.

Following the first interim review of data, and in line with Protocol Amendment 2, enrollment of new subjects into Arm A was suspended and enrollment into Arm B was permanently closed. Subjects in Arm B continued their current treatment or had their dose increased to 9.4 mg/kg at the investigator's discretion according to the guidance provided in Section 6 of protocol. Subjects in Arm A could have continued treatment at the investigator's discretion.

The second interim review was performed with a clinical cutoff that was 6 months after the clinical cutoff used for the first interim review. Following the second interim review, it was decided that enrollment in Arm A would be permanently closed.

The analyses specified in the SAP are considered the final analyses for the protocol, with a data cut-off of 18 months after the last subject was enrolled. Data collected in the extension phase will not be included in the analyses and will not be reported here. There will be a separate addendum with data from that phase.

The final decision for further development will be made based on the totality of data taking into consideration efficacy data, including spleen responses, symptoms, peripheral blood counts, bone marrow data, survival, safety, and PK/PD data.

1.3. Statistical Hypotheses for Primary Objectives

The primary hypothesis of this study is that the experimental treatment compared with historical data will significantly improve both spleen response rate and symptom response rate in subjects with intermediate-2 or high-risk MF relapsed/refractory to a janus kinase (JAK) Inhibitor.

Statistical Hypotheses are:

H₀: [REDACTED]

H₁: [REDACTED]

The null hypothesis is tested by the intersection-union test.¹ Each of the co-primary endpoints is tested at one sided $\alpha=0.025$, and the maximum Type I error rate for testing co-primary endpoints is the same as one sided $\alpha=0.025$.

1.4. Sample Size Justification

The study was planned to enroll approximately 200 subjects (approximately 100/arm) in the original protocol. As of result of decisions from the interim reviews, the study enrolled 107 subjects.

[REDACTED]

[REDACTED]
[REDACTED]
[REDACTED]

1.5. Randomization and Blinding

Subjects were centrally randomized to 2 dose regimens of imetelstat (9.4 mg/kg and 4.7 mg/kg imetelstat given intravenously [IV] every 3 weeks) in a 1:1 ratio based on a computer-generated randomization schedule prepared before the study. The randomization was stratified by a) spleen size ≥ 15 cm below the left costal margin by palpation (yes vs. no) and b) platelet count ($\geq 75 \times 10^9/L$ and $< 150 \times 10^9/L$ vs. $\geq 150 \times 10^9/L$) and balanced by using randomly permuted blocks.

The study was originally designed as a single-blind study, in which subjects would be blinded to the treatment arms. This was to reduce potential bias during data collection. Beginning with Protocol Amendment 2, enrollment of new subjects into Arm A (9.4 mg/kg) was suspended and enrollment into Arm B (4.7 mg/kg) was permanently closed. Any subject already in the Screening Phase at the time study enrollment was suspended, and who was subsequently determined to be eligible for the study, was allowed to proceed with treatment assignment to the 9.4 mg/kg arm per investigator discretion, subject agreement, and IRB/IEC notification. In addition, subjects were no longer blinded to treatment assignment. Data review committees and their access to data is detailed in Section [2.2.2](#).

2. ANALYSIS PLANNED

This analysis plan describes the planned efficacy and safety analyses for Study 63935937MYF2001 (hereafter referred to as Study MYF2001).

2.1. General Analysis Definitions

2.1.1. Baseline, Treatment Phase and Posttreatment Follow Up Phase

Unless specified otherwise, the baseline value is defined as the last non-missing value collected on or before the administration of the first dose of study drug. For subjects who have been randomized but not treated with any study drug, the randomization date will be used as the reference date for baseline value calculation.

The treatment phase begins on date of Cycle 1, Day 1 and continues until study drug discontinuation.

The Posttreatment follow up phase starts from the day after study drug discontinuation until death, lost to follow-up, withdrawal of consent or study end, whichever occurs first.

2.1.2. Visit Window

The following table will be used to generate derived visit based on relative day.

Parameter	Time Interval (label on output)	Time Interval (Day)*	Target Time Point (Day)
Vital signs	Baseline/0	<=1	1
	4	14 to 41	28
	8	42 to 69	56
	12	70 to 97	84
	:	:	:

For Visit = week 4k, target day is $4*k*7$, relative day is within window

$$4(k)*7-14 \leq \text{relative day} < 4k*7 + 14$$

2.1.3. Data Handling Rule and Imputation of Missing Data

In general, no missing data, other than missing dates specified below, will be imputed. For subjects who had dose escalation (from 4.7 mg/kg to 9.4 mg/kg), data up to dose escalation will be included in tables generated for CSR. Data after dose escalation (inclusive) will be listed only.

Imputation of partial missing dates will be made for AE onset date, AE resolution date, date of death, start and end dates of concomitant therapy, and date of initial diagnosis.

For AE onset and resolution date, the global standard AE imputation rules listed below will be applied.

Partial AE onset dates will be imputed as follows:

- If the onset date of an adverse event is missing day only, it will be set to:

- First day of the month that the AE occurred, if month/year of the onset of AE is different than the month/year of the first dose date
- The day of first dose date, if the month/year of the onset of AE is the same as month/year of the first dose date and month/year of the AE resolution date is different
- The day of first dose date or day of AE resolution date, whichever is earliest, if month/year of the onset of AE and month/year of the first dose date and month/year of the AE resolution date are same
- If the onset date of an adverse event is missing both day and month, it will be set to the earliest of:
 - January 1 of the year of onset, as long as this date is after the first dose date
 - Month and day of the first dose date, if this date is the same year that the AE occurred
 - The AE resolution date.
- Completely missing onset dates will not be imputed.
- Partial AE resolution dates not marked as ongoing will be imputed as follows:
 - If the resolution date of an adverse event is missing day only, it will be set to the earliest of the last day of the month of occurrence of resolution or the day of the date of death, if the death occurred in that month.
 - If the resolution date of an adverse event is missing both day and month, it will be set to the earliest of December 31 of the year or the day and month of the date of death, if the death occurred in that year.
 - Completely missing resolution dates will not be imputed.

For start and end dates of concomitant therapies, the global standard AE imputation rules listed above will be applied accordingly.

For date of death and date of initial diagnosis, the following rule will be applied.

- If date is completely missing, no imputation will be made.
- If year is missing, no imputation will be made.
- If only year is present but month and day are missing, then June 30th will be used.
- If only day is missing but year and month are available, then the 15th of the month will be used.

However, the above imputations will be modified by the following rules:

- If such imputed date for initial diagnosis is on or after study consent date, then consent date -1 will be used
- If the imputed date is for a date of death and is before the last date that the subject is known to be alive, the latter date + 1 will be used.

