2.3.8.4. Overall Survival

Definition

Overall Survival is measured from the date of Cycle 1, Day 1 to the date of the subject's death. If the subject is alive or the vital status is unknown, OS will be censored at the date that the subject is last known to be alive.

Analysis Methods

The Kaplan-Meier method will be used to estimate the distribution of OS for each treatment arm. One- and two-year overall survival rates, based on Kaplan-Meier estimates, for the 2 treatment arms will be presented, along with their 95% confidence interval.

Analysis based on the ITT population will be the core analysis for OS analysis. In addition, the following analyses for overall survival will be performed:

- 1) Overall survival time with censoring at dose escalation for subjects who were in Arm B and subsequently dose escalated to 9.4 mg/kg
- 2) Overall survival time with Rank Preserving Structural Failure Time (RPSFT) Method and Overall survival time with Inverse Probability of Censoring Weighting (IPCW) Method
- 3) Overall survival time excluding subjects who were in Arm B and subsequently dose escalated to 9.4 mg/kg
- 4) Overall survival time excluding subjects who were enrolled on or after Sept 9, 2016, when at the time study enrollment was suspended. Those subjects who were already in screening phase and subsequently determined to be eligible for the study, were allowed to proceed with treatment assignment to the 9.4 mg/kg arm per investigator discretion, subject agreement, and IRB/IEC notification.

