2.3.9.2. Death

Tabulations will be produced for all-cause mortality 30 and 60 days after the first dose, and within 30 days after the last dose, as well as all deaths for all subjects treated. The cause of death will also be summarized in this table. In particular, frequencies of deaths that are due to study treatment-related adverse events will also be reported.

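### SAP 2.1.3 cuts tabulated data of escalated Arm B subjects at escalation with no exception for survival or deaths, contradicting SAP 2.3.8.4 and 2.3.9.2

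*SAP*

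**What the plan says.** SAP 2.1.3 sets one rule for subjects whose dose rose from 4.7 to 9.4 mg/kg: "data up to dose escalation will be included in tables generated for CSR", and "Data after dose escalation (inclusive) will be listed only". No endpoint is exempted. The qualifier *in general* opens the preceding sentence, on missing data, and does not attach to this rule.

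SAP 2.3.8.4 gives OS its own definition. "Overall Survival is measured from the date of Cycle 1, Day 1 to the date of the" subject's death, and a subject who is alive or of unknown status is handled by the rule that "OS will be censored at the date that the subject is last known to be alive". Escalation is not a censoring event. "Analysis based on the ITT population will be the core analysis for OS analysis". Further analyses are then added, among them "Overall survival time with censoring at dose escalation for subjects who were in Arm B and subsequently dose escalated to 9.4 mg/kg" (analysis 1) and "Overall survival time with Rank Preserving Structural Failure Time (RPSFT) Method", which is paired with IPCW (analysis 2). One- and two-year Kaplan-Meier rates with 95% confidence intervals are reported for each arm.

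SAP 2.3.9.2 tabulates deaths in fixed windows "as well as all deaths for all subjects treated". SAP 2.3.5 defines time on study as OS with the censoring reversed, so it uses the same dates.

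**The concern.** An Arm B subject who escalates and later dies cannot be handled under all three sections at once. Under 2.1.3 that death appears in a listing only. Under 2.3.8.4 it is an event in core OS, and under 2.3.9.2 it is a row in the death table. Neither 2.1.3 nor 2.3.8.4 refers to the other.

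Two outputs are at stake. The first is the Arm B OS estimate. Protocol Section 6 restricts escalation to subjects who meet the entry limits for hematology and biochemistry, meet no dose-modification threshold and have had no earlier dose reduction. Those conditions plausibly select subjects with a better outlook, so stopping follow-up at escalation is plausibly informative and would tend to understate Arm B survival. The second is the death table, which would be incomplete whichever way any bias runs. SAP 1.2 says the development decision weighs survival and safety, so both outputs will be read.

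**Working it through.** **The text.** Take an Arm B subject who escalates and dies before the clinical cutoff.

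| Output | Under its own section | Under 2.1.3 taken literally |
|---|---|---|
| Core OS (2.3.8.4) | Event at death | No event; last known alive just before escalation, so censored there |
| Additional analysis 1 | Censored at escalation | Same |
| Analysis 2, RPSFT | Uses survival after escalation | Input removed |
| Analysis 2, IPCW | Censored at escalation and reweighted | Same |
| Analysis 3 | Subject excluded | Same |
| Analysis 4 | Event at death | Censored at escalation |
| Time on study (2.3.5) | Censored at death | Follow-up ends at escalation |
| Death table (2.3.9.2) | Counted | Missing |

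In the right-hand column core OS and analysis 1 coincide, apart from any gap between the last contact before escalation and escalation itself. Analysis 1 is then redundant and RPSFT cannot be run.

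**The size.** The plan gives no OS sample size, event count or power, no number escalated and no Arm B survival figure, so there is nothing to reproduce. SAP 1.4 gives 107 enrolled in total; protocol 3.2.1 gives 40 subjects in the 4.7 mg/kg arm in the first interim safety set. What follows is illustrative and every input is assumed.

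*Model 1.* Hazard for subject i = (ln 2 / m) × exp(0.7 u_i), with u_i standard normal and base median m of 15, 20 or 25 months. Administrative censoring falls uniformly at 18–30 months and escalation at 3–10 months. A fraction of 10%, 25% or 40% of the arm escalates, drawn from those alive at that time. Selection towards low u_i is none, moderate or strong. Dose has no effect on survival. Each setting has 200,000 simulated subjects. Kaplan-Meier two-year OS at m = 20, followed to death → cut at escalation:

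| Escalated | No selection | Moderate | Strong |
|---|---|---|---|
| 10% | 42.9% → 42.9% | 43.1% → 41.5% | 43.0% → 40.6% |
| 25% | 42.9% → 42.8% | 42.7% → 38.3% | 43.1% → 37.0% |
| 40% | 43.0% → 42.8% | 43.1% → 35.3% | 42.9% → 33.0% |

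One-year OS moves less: 62.7% → 60.7% (25%, moderate) and 62.9% → 58.4% (40%, strong). Over all three base medians with selection present, the fall in two-year OS runs from 49.3 − 47.8 = 1.5 points (m = 25, 10%, moderate) to 34.2 − 23.4 = 10.8 points (m = 15, 40%, strong), and 4% to 26% of Arm B deaths leave the analysis. With no selection the estimates agree within about 0.2 points, although 8% to 31% of deaths still leave.

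*Model 2, to test direction.* Gamma frailty with variance 0.7 and a true median of 18 months: S(t) = (1 + 0.7λt)^(−1/0.7), with λ = (2^0.7 − 1)/(0.7 × 18) = 0.6245/12.6 = 0.0496. Then S(24) = (1.833)^(−1.4286) = 0.42. With 24 of 48 subjects (an assumed arm size) escalated at months 2–8 and an assumed selection strength, cutting at escalation moves two-year OS from 42% to 33% if lower-risk subjects are likelier to escalate, leaves it essentially unchanged with no selection, and moves it from 42% to 50% if higher-risk subjects are likelier. The sign follows the selection assumed.

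**The case against.** The strongest reply is that the specific section governs the general one. SAP 2.3.8.4 defines OS completely, and its separate escalation-censored and RPSFT analyses make sense only if core OS runs past escalation. A careful programmer would probably follow it. This stands as evidence of intent, so a reader should not infer that core OS will in fact be the escalation-censored version. It does not remove the conflict. SAP 2.1.1 and 2.3.1 allow explicitly for other specifications elsewhere; the escalation rule in 2.1.3 does not. Section 2.1.3 also sets the imputation of death dates, so it cannot be read as having nothing to do with survival.

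The second reply concerns bias. A reader might infer that the cut necessarily lowers the 4.7 mg/kg curve and so inflates an apparent advantage of 9.4 mg/kg. The documents do not establish that. Within the eligibility limits escalation was at the investigator's discretion, and protocol 3.2.1 lets subjects who benefit but are not eligible for escalation stay on 4.7 mg/kg. Nothing says who was chosen among eligible subjects; inadequate responders are possible. The downward direction is a reasonable inference from the criteria, not a finding.

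Third, OS is a secondary, descriptive endpoint. Protocol 11.1 evaluates the arms independently and SAP 2.3.8.1.1 rules out a between-arm comparison. That is right, and it limits the consequence to reported estimates and tables.

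**Conclusion.** The contradiction is real and should be corrected. Applied as written, SAP 2.1.3 makes core OS equivalent to additional analysis 1, removes the data RPSFT needs, shortens time on study, and leaves deaths after escalation out of a table meant to hold them all. The likely intent is that of 2.3.8.4, but the SAP does not say so.

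Type I error and the co-primary tests are untouched. The effect falls on the Arm B one- and two-year OS rates, on any informal reading of the two arms together, and on the death table. For two-year OS, the assumed inputs give anything from no change to a fall of roughly 10 points, with a rise possible if higher-risk subjects were escalated. The figure cannot be narrowed without the number escalated and their prognosis. The gap in the death table depends on none of these assumptions, only on whether any escalated subject died.

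**What to change.** Add to SAP 2.1.3:

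> This cut does not apply to overall survival (2.3.8.4), time on study (2.3.5) or the death tabulations (2.3.9.2), which use all follow-up to death or the clinical cutoff; deaths after escalation are shown in a separately identified row. Within 2.3.8.4, follow-up is censored at escalation only in additional analysis 1 and in the IPCW part of additional analysis 2.

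IPCW is named because it censors at the switch by construction. The separate row keeps deaths after the dose change from being read without comment as deaths on 4.7 mg/kg. It also lets the death table be reconciled with the table of adverse events leading to death (2.3.9.1), which stays cut at escalation. The cost is two sentences in the SAP and one table row; no new data are needed.
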